The second secondary aim of our study is to “*Validate the Edmonton Frail Scale (EFS) as a screening instrument to identify frail patients and patients at risk of adverse events*” (see page 8).

The plan for the analyses was: “*The sensitivity and specificity of EFS in identifying frail patients will be tested against the full GA. EFS’ ability to predict adverse events on the defined outcomes will be assessed with uni- and multivariable regression analyses, controlled for relevant co-variates (e.g. type of cancer, stage of disease, and radiotherapy regimen*” (see page 17)

Partly based on the considerations stated under point 1, we have now decided to perform the validation by investigating the association between the instrument’s scores and OS in addition to association with GA findings. Another strong argument for this is that other well-known and widely used frailty screening instruments, e.g. the G8, have been widely tested against patients’ survival.¹⁻⁵ Thus, for comparison, which is important, we will do likewise.

Before embarking on these analyses, a detailed plan has also been prepared (**Appendix 2**).

3. We have decided not to use the term “frailty” when classifying the patients according to GA. Hence, we will not define the patients as frail or non-frail, but instead classify them according to their number of identified GA impairments.

Our primary hypothesis (page 8) has been revised accordingly, now reading: “*Our hypothesis is that increasing number of GA impairments is associated with increased risk of adverse events as defined, regardless of cancer type, stage, and radiotherapy procedure (localisation, dose, field size)*

This hypothesis and the primary aim of our study will be addressed in paper 3, for which a detailed plan for the analyses has also been prepared (**Appendix 3**)

This amendment also affects paper 2 as the sensitivity and specificity of Edmonton Frail Scale will be evaluated against number of geriatric deficits, not against a classification of frail vs. non-frail patients.

Explanation:

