Primary: Global quality of life (QoL) and physical function as assessed by the European Organisation for Research and Treatment of Cancer Quality of Life Questionnaire (EORTC QLQ-C30) global QoL (gQoL) and physical functioning (PF) scale.

Secondary:

- Instrumental Activities of Daily Living (ADL)-function assessed by Nottingham Extended Index of Activities of Daily Living (NEADL) based on patients' self-report.
- Role function as assessed by the EORTC QLQ-C30 role function (RF) scale
- Fatigue and pain as assessed by the EORTC QLQ-C30 corresponding symptom scales (FA = fatigue)(PA = Pain)

Exploratory: Functioning and symptom scales/items of the EORTC QLQ-C30 that are not defined as primary or secondary outcomes will be assessed for explorative purposes

Hypotheses:

1. Patients referred for palliative RT have poorer scores for all primary and secondary outcomes prior to and after RT compared to patients referred for curative treatment
2. There is a significant difference in trend in outcomes for palliative and curative patients:
 - a. patients referred for palliative RT will experience an improvement in the primary outcomes global QoL and PF, and the secondary outcomes RF, NEADL and pain (PA) within 8 weeks after RT.
 - b. patients referred for curative RT will experience a deterioration in the primary outcomes global QoL and PF and the secondary outcomes RF, NEADL and

fatigue (FA) scores from baseline to 2 weeks after RT. Thereafter the scores will return to baseline values within 16 weeks.

3. There is a significant difference in trend in outcomes depending on number of geriatric impairments
 - a. scores for the primary outcomes global QoL and PF, and the secondary outcome RF decreases with increasing number of geriatric impairments
 - b. there is a significant association between number of geriatric impairments and the primary outcomes global QoL and PF as well as the secondary outcome RF scores

Timeline for the assessments: Patients answered EORTC QLQ-C30 and NEADL at five different time points: baseline, when completing RT (except palliative patients who received only a single fraction were per protocol test schedule not asked to answer EORTC QLQ-C30, and patients who received <10 fractions were not asked to answer NEADL), and 2, 8 and 16 weeks after RT. We will exclude the assessment of NEADL at the end of RT from our analyses because patients with short courses of RT did not fill in this questionnaire.

Statistical approach

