Categorical baseline characteristics of curative and palliative patients will be described with frequencies and percentages, while continuous with means and standard deviations (SD) or median and min-max values.

Raw scores for all QLQ-C30 scales/items will be transformed into scales ranging from 0-100 in accordance with the official manual for this questionnaire. NEADL item scores will be summarized into a scale ranging from 0-66. Missing NEADL items scores will be imputed as follows:

The missing values are assumed to be missing at random (MAR), and will be imputed if at least half of the items of the scale had been answered. The imputation will be performed by generating an empirical distribution for each item based on non-missing values, and a random number drawn from it was used to replace the missing value.

To answer Study aim 1 and test our first hypothesis, the primary outcomes, global QoL and PF will be assessed by linear mixed model with fixed effects for (non-linear) time, treatment group (curative vs. palliative) and the interaction between the two. Random effects for patients will be included. The models will be adjusted for age, gender, performances status (ECOG PS) and cancer type. The secondary outcomes RF, NEADL and pain scores will be evaluated by similar models.

To answer Study aim 2 and test our second hypothesis, similar models to those describe for aim 1 will be performed for the primary outcomes global QoL and the secondary outcome RF. However, these models will use number of geriatric impairments as a stratification variable instead of treatment intent (palliative vs curative). The models will be adjusted for age, gender, cancer type, treatment intent (curative vs palliative) and ECOG PS.

Sensitivity analyses to estimate models for non-imputed variables for NEADL will be also be performed.

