For explorative purposes linear mixed model with fixed effects for (non-linear) time, treatment group (curative vs. palliative) and the interaction between the two will be estimated to assess differences in trend between palliative and curative patients for emotional function (EF, insomnia, appetite loss). Similar models will also be estimated to assess possible differences in trend in pain, fatigue, insomnia, and appetite loss between groups defined according to number of geriatric impairments. For these models number of geriatric impairments will be used for stratification instead of treatment intent. No adjustments will be made in any of the explorative models.

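### Pain and fatigue are declared secondary outcomes in Appendix 3, but their trends by number of geriatric impairments are planned only in unadjusted models, and fatigue has no adjusted model at all

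*Combined protocol and SAP*

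**What the plan says.** All of the following is in Appendix 3 (plan for paper 3).

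- **Outcome status.** Under Predefined outcomes, the secondary list includes "Fatigue and pain as assessed by the EORTC QLQ-C30 corresponding symptom scales". The exploratory category is what remains: "Functioning and symptom scales/items of the EORTC QLQ-C30 that are not defined as primary or secondary outcomes will be assessed for explorative purposes".
- **Adjusted models by intent (aim 1).** Global QoL and physical function, then role function, NEADL and pain, are modelled by curative versus palliative intent with adjustment for age, gender, ECOG status and cancer type. Fatigue is not in this list.
- **Adjusted models by impairment count (aim 2).** Global QoL and role function are named, and "The models will be adjusted for age, gender, cancer type, treatment intent (curative vs palliative) and ECOG PS".
- **Explorative models.** One set compares emotional function, insomnia and appetite loss by intent. The other is to "assess possible differences in trend in pain, fatigue, insomnia, and appetite loss between groups defined according to number of geriatric impairments". The section closes with "No adjustments will be made in any of the explorative models".
- **Hypotheses.** Hypothesis 1 expects poorer scores in palliative patients on every primary and secondary outcome. Hypothesis 2 expects different trends by intent: pain improving in palliative patients within 8 weeks (2a), and fatigue worsening in curative patients to 2 weeks after radiotherapy (2b). Hypothesis 3, on impairment count, names global QoL, physical function and role function only.

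**The concern.** By the plan's own definition, pain and fatigue are not exploratory outcomes, yet by impairment count they are handled as such and lose the covariates used in the sister models. No reason is given.

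This matters because the plan predicts one half of a confounding path: symptom level and symptom trend both depend on intent. The other half, an association between impairment count and intent, is plausible but undocumented. If palliative patients carry more impairments, 2a would make high-count groups appear to improve more on pain, and 2b would make low-count groups appear to worsen more on fatigue. Both distortions would flatter the patients with most impairments, in a study meant to find those at risk.

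Separately, hypothesis 2b makes a prediction about fatigue by intent, and no fatigue-by-intent model is named, adjusted or otherwise.

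**Working it through.** **No plan figure to reproduce.** The documents give no number for this comparison. The protocol's sample-size calculation concerns global QoL and physical function between frail and non-frail patients and plays no part here.

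**Step 1: which models are adjusted**

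| Outcome (all secondary) | By intent | By impairment count |
|---|---|---|
| Role function | adjusted | adjusted |
| Pain | adjusted | unadjusted only |
| Fatigue | no model named | unadjusted only |

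**Step 2: size of the possible bias**

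Suppose impairments have no effect. Split patients into a high-count and a low-count group (a simplification, since the plan does not give the grouping). Let D be the palliative-minus-curative difference in mean change. Then

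bias in the unadjusted count-by-time contrast = D × [P(palliative | high) − P(palliative | low)].

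Inputs:
- 165 curative and 136 palliative patients (Appendix 1).
- About 40% high count, borrowed from the protocol's 40% frail assumption.
- The split of high counts by intent, which is assumed.
- D, which is assumed at 10 or 20 points. For scale, the protocol takes 10 points on a QLQ-C30 scale as clinically significant.

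Worked row, with high count in 30% of curative and 50% of palliative patients:
- High group: 165 × 0.30 + 136 × 0.50 = 49.5 + 68 = 117.5. Palliative share 68 / 117.5 = 0.579.
- Low group: 115.5 + 68 = 183.5. Palliative share 68 / 183.5 = 0.371.
- Gap 0.208, so the bias is 2.1 points for D = 10 and 4.2 for D = 20.

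| High count, curative / palliative (assumed) | Gap in palliative share | Bias, D = 10 | Bias, D = 20 |
|---|---|---|---|
| 40% / 40% | 0 | 0 | 0 |
| 35% / 45% | 0.104 | 1.0 | 2.1 |
| 30% / 50% | 0.208 | 2.1 | 4.2 |
| 25% / 60% | 0.359 | 3.6 | 7.2 |
| 20% / 70% | 0.506 | 5.1 | 10.1 |

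**Step 3: what adjustment removes it**

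A simulation used the 30% / 50% row: 100 datasets, complete data, random-intercept mixed models, random-intercept and residual SD both 18, palliative patients 15 points higher at baseline, D = −10, and no true impairment effect.

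| Model | Mean count-by-time contrast | Mean baseline difference by count |
|---|---|---|
| Unadjusted | −2.42 | 3.49 |
| Intent as main effect | −2.42 | 1.42 |
| Intent-by-time added | −0.42 | 0.40 |

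The standard error of one estimated contrast is about 18 × √2 × √(1/117.5 + 1/183.5) = 25.46 × 0.118 = 3.0. Over 100 datasets the simulation error is about 0.3, so −0.42 is compatible with zero. All three models saw the same datasets, so the cleaner comparison is the difference −2.42 − (−0.42) = −2.00, close to the −2.08 from the formula.

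A second run, with more dropout in palliative patients, gave −1.45, −1.44 and 0.70. The corresponding difference is −2.15, again close to the formula.

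In both runs, intent as a main effect reduced the baseline difference but left the trend contrast essentially unchanged. The intent-by-time term removed about 2 points.

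**The case against.** The strongest reply is that these models are openly declared explorative and unadjusted. Crude trajectories by impairment count are a legitimate description in a project that wants to know who is at risk, and they mislead only if reported as independent effects. That stands, and it limits the severity. It does not explain why two outcomes that the plan itself ranks as secondary are put in that class.

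Several stronger readings are tempting, and the documents do not support them:

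- **All explorative models are confounded by intent.** In the set for emotional function, insomnia and appetite loss, intent is the exposure. Only age, gender, cancer type and ECOG status could confound there.
- **Confounding is established.** The documents report no association between impairment count and intent or cancer type. With none, the bias is zero. Only the most extreme assumed row with D = 20 reaches 10 points.
- **The revised primary hypothesis is compromised.** Amendment 4, point 3 concerns the adverse events defined under Study aims: reduced QoL, physical deterioration, more need for help, and residential care. Pain and fatigue are not among them, nor are they in hypothesis 3. The protocol's general promise of adjusted models for secondary outcomes does not clearly reach them either, because its secondary outcomes are NEADL and admissions.
- **Pain is left without any adjusted model.** Pain by intent, the comparison that hypothesis 2a makes, is adjusted.
- **Copying the aim 2 covariates would be enough.** Step 3 shows that a main effect of intent leaves a trend contrast as it was. The aim 2 text names no intent-by-time term, so the same limit applies to those models.

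**Conclusion.** The point holds in a limited form. Appendix 3 is inconsistent about pain and fatigue: they are secondary by declaration, but explorative and unadjusted by impairment count. Fatigue has no adjusted model despite hypothesis 2b. Because the plan expects level and trend to differ by intent, the unadjusted count-by-time contrasts may partly reflect palliative versus curative intent.

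The size is about 0 to 5 points per 10-point difference in change between intent groups. This rests on a two-group split, about 40% high count, and assumed imbalances from none to 20% versus 70%. Whether any bias exists depends on a count-intent association that the documents do not give. Severity is low: no stated figure and no count hypothesis changes, and the harm arises mainly if pain or fatigue by count is reported as a secondary-outcome finding.

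**What to change.** Amend the Statistical approach in Appendix 3 as follows:

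1. Exempt pain and fatigue by impairment count from the no-adjustment sentence. Fit them with the aim 2 covariates (age, gender, cancer type, treatment intent, ECOG status) plus an intent-by-time term.
2. Add fatigue to the adjusted curative-versus-palliative models for secondary outcomes, so that hypothesis 2b has a named analysis.
3. Report the unadjusted pain and fatigue estimates by count as supplementary description, labelled as such.

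The explorative curative-versus-palliative models need no change on this ground. The cost is wording and a few extra model fits. The covariates are already collected and already used in the parallel models, so no new data are needed.
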